The first exploratory objective of the Stage 2 study is to determine the pro-kinetic effect of repeated oral doses of ENT-01 on colonic motility as determined by Sitzmarks capsule retention. The Sitzmarks test will be performed on days 1-5 of the two-week run-in period and again at the end of the randomized treatment period.

The exploratory objectives will be to collect information on the effect of orally administered ENT-01 on sleep, temperature, memory, energy and mood in patients with Parkinson's disease. During the study, all patients will maintain a daily sleep diary. They will record bed time, sleep time and morning waking, hours slept each night, number and duration of wakes, and leg twitching/thrashing during the night. In addition, we will evaluate sleep indirectly using an I-Button which measures skin temperature. Diurnal variations in temperature correlate well with the sleep-wake cycle (Sarabia et al., 2008; van Marken Lichtenbelt et al., 2006). The patients will be asked to wear the I-Button attached to a wrist-band for five consecutive 24 hour periods during the baseline period (Period 3.1), during the stable-dose period (Period 3.2), the randomized period (Period 4) and part of the wash-out period. They will remove it only during showering. Mood, fatigue, hallucinations, memory and executive function will all be assessed at baseline, during the fixed dose period and at the end of the randomization period using the Beck Depression Index (BDI), REM behavior disorder questionnaire (RBDQ), Parkinson Fatigue Scale (PFS-16), University Miami Parkinson Disease Hallucination Questionnaire (UM-PDHQ), NMS questionnaire (NMS), MMSE and Trail-making A and B), respectively.

Primary Efficacy End-point:

The primary efficacy end-point will be regularization of bowel function as determined by stool frequency. This will be defined as an increase in frequency by one or more spontaneous, complete bowel movement per week compared to baseline or three or more spontaneous, complete bowel movements per week. Assessment will occur at the end of the fixed-dose period (Period 3.2) and baseline will be obtained at the end of the run-in period (Period 3.1) and all patients (n=40) will be compared with their baseline bowel function. During the randomized period (Period 4) the treatment group will be compared to the placebo group using the same criteria (n=20 in each group).

Summary of success criteria: (at least one of the following is met)

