4.5 Discontinuation Criteria

Patients may withdraw voluntarily from participation in the study at any time and for any

reason. They may want to withdraw because of increased constipation off laxatives, nausea,

vomiting or diarrhea.

Patients may be withdrawn on the basis of the medical monitor safety and tolerability

review or the Investigator's clinical judgment, protocol deviation, change in dose of medications

unrelated to study medication or loss to follow-up.

This study may be terminated at the discretion of the Enterin, Inc. or of any regulatory

agency for reasons including safety and/or efficacy.

An Investigator may elect to discontinue or stop the study at his or her site for any reason

including safety.

When a patient withdraws or is withdrawn before completing the study, the date and reason

for withdrawal are to be documented in the eCRF. The study site must immediately notify the

medical monitor. Patients who withdraw prematurely are to attend an early discontinuation visit

if possible, at which time they will complete all assessments.

In the event that a patient is withdrawn prematurely due to an AE or serious AE, the AE or

serious AE will be followed until it resolves or stabilizes, or until it is judged by the Investigator

to be no longer clinically significant.

CP1001 v0.9, Version Date: 27JUL2017

41

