10 DATA MANAGEMENT AND STATISTICS

This is a trial with two stages. The Stage 1 portion will consist of 10 patients who will be dose escalated in single doses. Each patient will proceed through all the dose escalations starting at 25 mg and ending at 200 mg or at the dose at which s/he experiences a dose limiting toxicity (DLT). The doses to be tested are 25mg, 50mg, 75mg, 100mg, 125mg, 150mg, 175mg and 200mg. In the Stage 2 portion, all patients will go through a multiple dose escalation (3 dosing days at each dose) and the dose at which the patient experiences a consistent pro-kinetic effect (spontaneous, complete stool in at least 2/3 consecutive doses) without a DLT will be the dose for that patient. Patients who experience a DLT prior to reaching their pro-kinetic dose and at a dose equal to or less than the STDE dose will be terminated. Otherwise the patient will be assigned the highest dose at which they did not experience a DLT. If the patient reached 175 mg without a DLT and without a pro-kinetic dose, her/his dose will be 175 mg. The primary endpoint for the Stage 1 study is to determine whether the dose levels explored are safe and tolerable. The primary endpoint for the Stage 2 study is the regularization of bowel function as determined by stool frequency at the end of the fixed dose period compared to baseline. The Stage 2 portion will enroll 40 patients, with a target sample size of 34 evaluable patients. Six extra patients are enrolled to allow for patient withdrawals or terminations prior to the completion of the trial.

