The target sample size for Stage 2 is 34 evaluable patients and an additional 6 patients will be accrued to allow for patient drop-outs and terminations; these 40 patients will be different from the 10 patients accrued to Stage 1. A patient is evaluable if s/he has baseline measurements (obtained at the end of the run-in Period, 3.1) and measurements at the end of the fixed dose period (end of Period 3.2). The primary endpoint for Stage 2 is average complete spontaneous stool frequency increase by 1 point over baseline, OR 3 or more complete spontaneous stools per week. A patient will be labeled as a "success" if s/he meets one or more of the criteria above, otherwise the patient will be labeled as a "failure". The primary analysis compares the proportion of patients deemed a success at the end of the fixed-dose period (end of period 3.2) to 0.10, which is the highest proportion of spontaneous resolution of constipation assuming no treatment. A patient is deemed a success or failure by comparing the assessment at the end of the fixed-dose period (Period 3.2) to baseline (obtained at the end of the run-in period, Period 3.1). There could be between 34 and 40 patients with these measurements and each patient will be labeled as a "success" or "failure". It is assumed that without treatment, the success rate would be 10% (null hypothesis). An exact binomial test with a 0.05 two-sided significance level will have 80% power to detect the difference between 0.10 (proportion expected if patients are not treated), p₀, and an ENT-01 proportion, p_E , of 0.29 (0.27) when the sample size is 34 (40). It is assumed that most patients will be deemed a success on the ENT-01 arm and so the study is adequately powered.

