10.3.2 Efficacy Endpoints

Frequency of bowel movements:

The frequency of bowel movements will be determined via a daily diary where the passage of a bowel movement or absence thereof will be recorded daily throughout the study. *Bowel movements that are the consequence of a rescue medication or suppository will not be counted if they occur within 24 hours of the rescue medication or suppository.* Episodes of incontinence will also be recorded.

Success will be defined as an average complete spontaneous stool frequency increase by 1/week or more compared to baseline or 3 or more complete spontaneous stools/week. Baseline will be the run-in period weekly average and treatment period will be determined as the weekly average during the fixed dose (40 patients) treatment period.

Colonic Motility:

Colonic motility will be determined using the Sitzmarks technique at the beginning of the run-in period and again at the end of the randomized treatment period during Stage 2. The primary measure of interest is the mean colonic transit (MCT) time estimated with a single film (Metcalf et al., 1987).

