10.4 Analysis Plan

10.5 Stage 2

Primary analysis: The AE information for the Stage 2 portion of the trial will be summarized as frequency and relative frequency by each dose level and for the LSTDEi for each person.

The primary efficacy outcome variable is whether or not a patient is a "success" or "failure". This is an endpoint based on patient diary entries for the week prior to the endpoint assessment defined as average complete stool frequency increase by 1 or more over baseline, OR 3 or more complete spontaneous stools/week. The patient is deemed a "success" if s/he meets one or more of the criteria listed above, otherwise the patient will be deemed a "failure". The primary analysis will be based on all patients with a baseline assessment (the end of the run-in period, Period 3.1) and an assessment at the end of the fixed-dose period (Period 3.2) and will be a comparison of the proportion of successes with 0.10 (the null hypothesis corresponding to no treatment effect). The proportion of patients for whom the drug was a success at the end of period 3.2 will be estimated with a binomial point estimate and corresponding 95% confidence interval. The observed proportion of successes will be compared to 0.10 using an exact binomial test. ENT-01 will be deemed as demonstrating sufficient efficacy if the two-sided p-value is less than 0.05 for this comparison.

Secondary analyses:

A secondary analysis will compare the proportions of patients who are deemed a success at the end of the randomized period (Period 4) as compared to baseline (end of the run-in period, Period 3.1) between those randomized to the ENT-01 arm and those randomized to the placebo arm. Patients to be included in this analysis will be those who have a baseline assessment (end of the run-in period) and an assessment at the end of the randomization period of the trial, which could be between 34 and 40 patients (17 to 20 in each arm). A Fisher's exact test will be used to compare the proportions of patients who are deemed a success at the end of randomization period (period 4) between the two randomized arms. Another secondary analysis will compare the proportions of patients who are a success (compared to baseline) between the end of the first week of the washout period (period 5) to the end of the randomization period (period 4), for those

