The protocol dated 27 July 2017 was amended during the trial. And the protocol amendment was finalized on 02 February 2018. In this amendment, Stage 2 dose range is from 100 mg to 250 mg with an increment 25 mg for next higher dose. It also removed randomization period.

Except for the above changes, there were no other changes from protocol dated 27 July 2017

Table 1: Overall Study Design

Period 1	STAGE 1			STAGE 2A			Period 5
	Period 2.1	Period 2.2	Period 3.1	Period 3.2	Period 4	Period 5	
Run-in sentinel group (Cohort 1)	Single dose escalation sentinel group	Washout	Run-in (Cohort 2)	Identification of prokinetic dose using a 10 subject sentinel group followed by the remaining subjects	1:1 Randomization onto placebo or prokinetic dose	Washout	
2 weeks N=10	3 weeks N=10	2 weeks N=10	2 weeks N=40	≤17days N=40	6 days N=40	2 weeks N=40	

Table 2: Schedule of Assessments of Stage 1

Period	1 Run-In Sentinel 2 wks		2.1 Single Dose 3-8 wks	2.2 Wash-Out 2 wks
	D1	D14	D1	
Consent	X			
Demographics	X			
Inclusion/exclusion	X	X		
Medical history	X			
Physical exam	X		X	X
Vital signs ¹	X		X	X
Rome-IV	X			
Blood chemistry	X		X	X
Hematology	X			
Urinalysis	X			X
Fecal occult blood	X		X	X
EKG	X		X	X
Pregnancy test	X			
Monitoring			X	X
Discontinue medications	X			
Re-start medications				X
Diary entries	X	X	X	X
UPDRS	X		X ⁴	X ²
I-Button ³	X	X	X	
PAC-QOL	X	X	X ⁴	X ²
PAC_SYM	X	X	X ⁴	X ²
RBDQ	X		X ⁴	X ²
NMSQ	X		X ⁴	X ²
PFS-16	X		X ⁴	X ²
UM-PDHQ	X		X ⁴	X ²
BDI	X		X ⁴	X ²
Trail-making A and B	X		X ⁴	X ²

Table 2: Schedule of Assessment of Stage 1

Period	1 Run-In Sentinel 2wks		2.1 Single Dose 3-8 wks	2.2 Wash-Out 2 wks
	D1	D14		
MMSE	X		X ⁴	X ²
Adverse events		X	X	X
PK samples			X ⁵	
Schedule visit days	X			
Administer ENT Dose			X	
Record Medications	X	X	X	X
Daily phone calls to on non-visit days		X	X	X

¹Vital signs taken before dose and 2 hours after dose

²End of period 2

³I-Button placed days 9 of run-in periods and worn continuously through day 5 of wash-out periods.

⁴Surveys taken at last dosing visit

⁵PK samples taken pre-dose and 1, 2, 4, 8 and 24 hours post-dose

Table 3: Schedule of Assessments of Stage 2 under Protocol Dated 27 July 2017

Scheduled Assessments	Period 3.1 Run-In					Period 3.2 Multiple Dose		Period 4 Randomized Treatment			Period 5 Wash-Out	
	Day 1 Visit 1	Days 2-7, 9- 10, 12-13 Calls	Day 8 Call	Day 11 Visit 2	Day 14 Call	Days. 1-13, 15-16 Calls	Day 14 Call	Day 1 Visit 3 ⁶	Days 2-5 Calls	Day 6 Visit 4	Days 1-7 Calls	Day 14 Visit 5

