2.2 Sample Size/ Power Calculation

No formal sample size calculation was performed for Stage 1. The number of subjects is based on feasibility and is considered sufficient to meet the objectives of the study.

For Stage 2, assuming the highest proportion of spontaneous resolution of constipation with no treatment to be 0.10, 34 evaluable subjects who have measurements at both baseline and at the end of the fixed dose period will provide 80% power to detect the difference between 0.10 (proportion expected if patients are not treated), p_0 , and an ENT-01 proportion, p_E , of 0.29. Assuming a drop-out rate of 15%, a total of 40 subjects will ensure at least 34 evaluable subjects will be obtained.

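### The Stage 2 primary success rate is defined on patients with an end-of-fixed-dose assessment, and no rule says how to score dosed patients who leave during titration, so the single-arm estimate can be biased upward.

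*Protocol*

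**What the plan says.** **Protocol.** Section 10.5 bases the primary test on patients with both a baseline and an end-of-fixed-dose assessment ("based on all patients with a baseline assessment (the end of the run-in period, Period 3.1) and an assessment at the end of the fixed-dose" phase). Section 10.1.2 defines an evaluable patient the same way and adds "There could be between 34 and 40 patients with these measurements". Its success-or-failure labelling is applied to those patients. Section 10 gives the reason for enrolling 40: "Six extra patients are enrolled to allow for patient withdrawals or terminations prior to the completion of the trial". Two other places refer to all 40: Section 2.2 ("all patients (n=40) will be compared with their baseline bowel function") and Section 10.3.2 ("weekly average during the fixed dose (40 patients) treatment period"). Neither says how a patient without a fixed-dose value is scored.

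**SAP.** Section 2.2 keeps the evaluable definition for sizing: "34 evaluable subjects who have measurements at both baseline and at the end of the fixed dose period will provide 80% power". Section 7.7.2 compares the proportion of successes at the end of the fixed period with 0.10 by an exact binomial test, but ties its summaries only to whichever population is appropriate. Section 6.3 defines a Full Analysis Set of treated subjects with a baseline and at least one post-baseline stool diary. Section 7.1 bases percentages on non-missing values and does not impute. Section 8.3 in general does not impute missing diaries. The early-termination rule in Section 8.2 concerns safety measurements. Section 5.1 reports no changes from the protocol's analyses, and Section 9 lists dropped secondary analyses only.

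**Reasons for leaving.** Protocol 4.5 names reasons for voluntary withdrawal, beginning "They may want to withdraw because of increased constipation off laxatives, nausea" and going on to vomiting and diarrhea. The individual stopping criteria in Period 3.2 (Section 3.1) terminate patients who reach a dose-limiting event before a pro-kinetic effect. The Period 4 text says the 15% allowance includes losses for tolerability.

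**The concern.** A patient who takes ENT-01, tolerates it poorly or sees no benefit, and leaves before any fixed-dose diary day has no value for the primary endpoint. As the plan is written, that patient is dropped instead of being counted as a failure. If such patients would have succeeded less often than those who stayed, the reported proportion describes people who got through titration and overstates success among people who started the drug.

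In a randomized comparison a similar selection in both arms might partly cancel. Here the comparison is with a fixed 0.10. After the amendment removed the randomized period, this is also the only formal efficacy test that the SAP specifies.

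**Working it through.** **1. Inputs.** Null rate 0.10, exact binomial test, two-sided 0.05, alternative 0.29 at n = 34 and 0.27 at n = 40 (Protocol 10.1.2). Dropout 15%, 40 to 34 (Protocol 4.1, SAP 2.2). Assumption: all 40 take at least one dose and every loss occurs in titration. The documents do not give the timing of losses, and some could precede dosing.

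**2. The plan's own figure.** The smallest significant count is 8 of 34 and 9 of 40. Power = P(X ≥ 8 | 34, 0.29) = 81.2% and P(X ≥ 9 | 40, 0.27) = 79.1%. Both agree with the stated 80%.

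**3. Size of the bias.** Let a be the number assessed, m the number dosed but not assessed, and f the leavers' success rate as a fraction of the completers' rate. The completer estimate exceeds the all-dosed rate by the factor (a + m)/(a + f·m).

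| 40 dosed, assessed a = | 34 | 35 | 36 | 37 | 38 | 39 |
|---|---|---|---|---|---|---|
| Ceiling, f = 0: 40/a | 1.18 | 1.14 | 1.11 | 1.08 | 1.05 | 1.03 |

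| a = 34, m = 6, f = | 0 | 0.25 | 0.5 | 0.75 | 1 |
|---|---|---|---|---|---|
| 40/(34 + 6f) | 1.18 | 1.13 | 1.08 | 1.04 | 1.00 |

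The documents do not give f. Illustration at the ceiling: 17/34 = 50.0% (exact 95% CI 32.4 to 67.6) against 17/40 = 42.5% (27.0 to 59.1).

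**4. Effect on the decision.** Two-sided p-values for 8 successes, by the two usual exact conventions:

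| n | 34 | 35 | 36 | 37 | 38 | 39 | 40 |
|---|---|---|---|---|---|---|---|
| Minimum likelihood | 0.017 | 0.020 | 0.024 | 0.027 | 0.0501 | 0.053 | 0.057 |
| Doubled tail | 0.034 | 0.040 | 0.047 | 0.055 | 0.064 | 0.073 | 0.084 |

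Seven successes are not significant at n = 34 (p = 0.076 and 0.096). Nine are significant at n = 40 (0.016 and 0.031). So with 34 to 40 assessed and at most 40 dosed, the decision can change only at 8 successes. Below 34 assessed it can also change at lower counts: by minimum likelihood 7/33 gives p = 0.042, while 7/34 gives 0.076.

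The chance of exactly 8 successes with 34 to 37 assessed is 12.3% to 9.4% at a completer rate of 0.29, 2.0% to 0.9% at 0.40, and about 0.1% or less at 0.50.

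**5. Power with leavers scored as failures.** The threshold is 9 of 40. If each patient has a 15% chance of loss, the all-dosed rate is 0.85 times the completer rate: P(X ≥ 9 | 40, 0.85 × 0.29) = 68.2%. It is 79.9% at a completer rate of 0.32 and 99.8% at 0.50. With a fixed number assessed out of 40 dosed and a rate of 0.29, it is 69% (34 assessed), 76% (36), 81% (38) and 86% (40).

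**The case against.** **The SAP does not state an exclusion.** A reader might infer that the SAP expressly restricts the test to completers. It does not. It supersedes the protocol's statistical section, and its Full Analysis Set can include titration leavers who kept a diary. The exclusion on the SAP side follows from an unnamed population, non-missing denominators and no imputation. This stands, and it narrows the claim: the SAP leaves leavers unscored.

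**Whether the protocol wording survived the amendment.** One could lean on the SAP's statement "Except for the above changes, there were no other changes from protocol dated 27 July 2017". That is weak support. SAP Table 4, for the amended protocol, has no Sitzmarks or X-ray rows, makes Period 4 the fixed-dose period and adds a Day 28 call. The amendment is not among the documents. The point therefore rests on the July 2017 protocol and on the SAP's own text.

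**Few exits may be outcome-related.** Non-responders at the top dose stay in and count as failures. Someone who stops partway through fixed dosing can still have a value, because rates are per diary day. Some withdrawals, such as those from stopping laxatives, may come in run-in before any dose. Missing the pro-kinetic criterion (a complete spontaneous stool on two of three days) is also not the same as failing the endpoint (one more per week than baseline, or three per week). All of this stands: f near zero is not established, and 1.18 is a ceiling.

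**Early phase.** The Stage 2 primary objectives are safety, tolerability, PK and PD, the protocol openly sizes on evaluable patients, and disposition by period and reason is planned. That limits the seriousness. It does not supply a scoring rule for the primary efficacy endpoint.

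**Conclusion.** The point holds in this form: followed as written, the plan gives dosed titration leavers no success value and removes them from the primary proportion, and neither document contains a rule or sensitivity analysis that counts them. The success rate can be overstated by up to 1.18-fold. That ceiling assumes 40 dosed, 6 lost in titration, and none of the 6 a would-be success. With fewer losses, or leavers who do as well as completers, the bias shrinks to nothing.

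A reader might infer that a significant result could be produced by this exclusion. With 34 to 40 assessed that is possible only at 8 successes, which is unlikely at the high success rate the protocol expects. A reader might also infer that the decision can never change at any other count; that fails once fewer than 34 are assessed. What is mainly affected is the estimate and its confidence interval. It should be fixed, but it does not by itself undermine the test.

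**What to change.** In SAP 7.7.2:

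- Name all Stage 2 patients who took at least one dose of ENT-01 (the Safety population, SAP 6.2) as the primary denominator.
- Score a patient with no fixed-dose value as a failure.
- Report the completer proportion with its confidence interval as a sensitivity analysis.
- Restate the power in Protocol 10.1.2 and SAP 2.2 on that denominator, using the figures in step 5 above.

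This changes wording only. It needs no new data, and the disposition counts and reasons in SAP 7.2.4 already support it. The price is that failure scoring is conservative when losses have nothing to do with the drug, and that power falls from 81% to about 68% at a completer rate of 0.29 with 15% lost. About 0.32 is then needed for 80%. At 0.50 power stays above 99%.

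Separately, the termination wording must be reconciled, because it decides who has an endpoint. In Protocol 3.1, the Period 3.2 narrative terminates for a dose-limiting event at the STDE dose. The tolerability paragraph terminates when the STDE was the highest dose without such an event. The individual stopping criteria terminate for any such event before effect. The Period 4 text refers to a tolerability limit below the STDE, and Section 10 to an event at or below it. Which rule applies is for the sponsor to settle.
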